6.4 Evaluation at time of presumptive or diagnosed GC, CT and syphilis

6.4.1 Symptoms suggestive of STI for which presumptive STI treatment will be administered.

For those who have symptoms of an STI at a study visit given characteristic clinical presentation (such as chancre, rash characteristic of syphilis, symptomatic urethritis or proctitis) such that the treating clinician will provide empiric STI treatment while awaiting confirmatory testing, standard STI testing should be obtained from urine/pharynx/rectum for GC/CT and blood for syphilis testing. In addition, the following specimens should be obtained for resistance testing from symptomatic anatomic sites based on the clinical presentation as outlined in Table 6.4.1.

NOTE: For specimens collected due to presumptive infection, the resistance testing specimens (swabs/urine collection) should be held until definitive STI testing is available. If STI testing indicates no infection, the specimens may be discarded. Alternatively, the site may send all specimens for storage. Specimens that are not associated with a confirmed STI will be discarded when the data management team confirms absence of STI. If there is uncertainty about whether STI if present, the specimens should be sent to the BioHUB for testing.

NOTE: Testing for evidence of resistance to GC, CT and syphilis should be conducted prior to STI treatment. If collection of specimens before treatment is not possible, CT and syphilis testing can be conducted the same day of treatment after treatment has been provided. Per the SURRG protocol, GC cultures should only be collected before GC treatment.

Table 6.4.1 Specimen collection for resistance testing at time of evaluation for STI and presumptiveSTI treatment

Presumptive infection		Specimen collection						
	Buccal Swab (Zymo)	Rectal Swab (Zymo)	Urine (Zymo)	Urine (Hologic urine specimen for M.gen)	Swab of chancre/ mucosal lesion (Zymo)	GC culture per local protocol (all anatomic sites of sexual exposure in past 90 days)		
Urethritis			\checkmark	\checkmark		(urethral discharge)		
Proctitis		\checkmark				\checkmark		
Syphilis with chancre/mucosal legion					\checkmark			
Syphilis diagnosis without chancre/mucosal lesion	\checkmark							

6.4.2 Documented STI:

Individuals with positive GC and/or CT NAAT results or with serologic testing indicating a new syphilis infection will be contacted to return for STI treatment as well as swabs of affected site for resistance testing or urine collection, as outlined in Table 6.4.1 Specifically:

- Those with positive GC NAAT results will have
 - 1) a swab obtained from the involved anatomic site and other sites of sexual contact in past 90 days (to include throat, rectum, urine) if indicated for GC culture-based phenotypic testing according to local GC culture protocol, and
 - 2) a swab/urine sample obtained from anatomic site of infection only for molecular resistance testing.
- For those with CT infection, a swab or urine specimen will be collected (depending on the site of infection) for molecular resistance testing.
- For those with confirmed rectal or pharyngeal CT, a swab will be collected for chlamydia cell culture. Please see MOPS for specimen handing instructions.
- For those with syphilis serologies indicating new infection and in whom no chancres/mucosal lesions are present, a buccal mucosal swab will be obtained for *T. pallidum* DNA amplification which, if positive, will be used for resistance testing. If suspected syphilitic chancre is present, this should be swabbed for molecular testing

Documented STI			Specimen collection						
	Buccal Swab (Zymo)	Pharyngeal Swab (Zymo)	Rectal Swab (Zymo)	Rectal or pharyngeal swab (Culture)	Urine Collection (Zymo)	Swab of chancre (Zymo)	GC culture per local protocol (all anatomic sites of sexual exposure in past 90 days		
Chlamydia		$\sqrt{*}$	$\sqrt{*}$	$\sqrt{*}$	$\sqrt{*}$				
Gonorrhea		√*	√*		$\sqrt{*}$		\checkmark		
Syphilis with chancre/mucosal legion						\checkmark			
Secondary syphilis (rash)									

*Specimen sent from site of confirmed infection only

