1.2.5 Rationale for evaluation of nongonoccal urethritis (NGU) and Mycoplasma genitalium (MG)

Mycoplasma genitalium is a frequent cause of urethritis in men .⁵¹ MG can be detected with nucleic acid testing; however, many public health programs do not routinely test for MG and instead treat non-gonoccocal urethritis (NGU) empirically.⁵² While azithromycin is superior to doxycycline for treatment of MG, ^{53, 54} doxycycline does have activity against MG and use of doxycycline PEP may potentially impact the prevalence of MG, the incidence of MG-associated urethritis and the syndrome of NGU. Therefore, urine will be collected every three months to look for the presence of asymptomatic MG as well as at the time of urethral symptoms, to evaluate for MG as the etiology of urethritis.^{53, 54} Specimens with MG detected will be stored for future analysis of resistance to tetracycline and other antimicrobials.

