3.3 Exploratory objectives

- 3.3.1 Evaluate the diversity of the gut microbiome and quantity and breadth of drug resistance genes in participants on doxycycline PEP and not on PEP
- 3.3.2 Assess the association between meningococcal vaccination and incident GC infection
- 3.3.3 Evaluate the incidence of urethritis without identified bacterial etiology and the proportion which is associated with MG in each arm
- 3.3.4 Assess the rate of detection of *Mycoplasma genitalium* (MG) in urine in each arm and the presence of tetracycline and other antimicrobial resistance in MG in each arm.
- 3.3.5 Evaluate association of doxycycline use with weight change over time
- 3.3.6 Evaluate whether doxycycline PEP is associated with PrEP persistence and HIV virologic suppression by comparison of arms and within the doxycycline PEP arm by adherence to doxycycline PEP.
- 3.3.7 Evaluate the incidence of lymphogranuloma venereum (LGV) in those diagnosed with rectal chlamydia in each arm

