6 CLINICAL AND LABORATORY MONITORING

6.1 Schedule of Events

Month (+2/-10 week window)	0	3	6	9	12 or Termination visit	Doxycycline initiation visit for those in control arm
Informed consent	\checkmark					\checkmark
Smartphone app instructions	\checkmark					
Review of current medications		$\sqrt{*}$	$\sqrt{*}$	$\sqrt{*}$	$\sqrt{*}$	\checkmark
Antibiotic & STI history	\checkmark	\checkmark	\checkmark	\checkmark		
Meningococcal vaccination history						
Sexual behavior questionnaire	\checkmark	\checkmark	\checkmark	\checkmark	\checkmark	
Dispense pills/adherence counseling*	$\sqrt{*}$	$\sqrt{*}$	$\sqrt{*}$	$\sqrt{*}$		\checkmark
Doxycycline pill count and adherence recall*		$\sqrt{*}$	$\sqrt{*}$	$\sqrt{*}$	√*	
Doxycycline PEP acceptability survey*			$\sqrt{*}$		$\sqrt{*}$	
General symptom assessment	\checkmark	\checkmark	\checkmark	\checkmark		
Costing questionnaire		\checkmark	\checkmark	\checkmark		
Condoms/lubricant	\checkmark	\checkmark	\checkmark	\checkmark		
Risk reduction counseling	\checkmark	\checkmark	\checkmark	\checkmark		
GC/CT testing (throat & rectal swab, urine collection)	\checkmark	\checkmark		\checkmark	\checkmark	
Syphilis testing	\checkmark	\checkmark	\checkmark	\checkmark	\checkmark	
Rectal swabs stored for future microbiome testing, all participants	\checkmark		\checkmark		\checkmark	\checkmark
Rectal swab stored for future MG testing	\checkmark	\checkmark	\checkmark	\checkmark	\checkmark	
Urine stored for future MG testing (also at time of symptomatic urethritis)	\checkmark	\checkmark	\checkmark	\checkmark	\checkmark	
Swabs/urine at time of evaluation for STI symptoms or confirmed STIs for resistance testing		at time	e of evalua	ation for S	STI symptoms or	r confirmed STI
Anterior nares and oropharyngeal swabs for Staphylococcus aureus culture	\checkmark		\checkmark		\checkmark	
Oropharyngeal swabs for cultures of Neisseria species	\checkmark				\checkmark	
Stool sample from first 50 PLWH & first 50 HIV- on PrEP*	$\sqrt{*}$		$\sqrt{*}$		√*	
Collection of hair for doxycycline testing			\checkmark		\checkmark	

DoxyPEP protocol Ver 9.0 5/27/2022

(subset of participants, optional) *Inter	*Intervention arm only **Standard of care arm only						
Qualitative interviews*				3-12	2 months	• •	
Weight	\checkmark	\checkmark	\checkmark	\checkmark			
Reimbursement	\checkmark	\checkmark	\checkmark	\checkmark			
Stored serum for future testing (Optional)	\checkmark				\checkmark		

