6.3.13 Urine for *M.genitalium* testing

At the time of urine collection for GC/CT testing, a sample of this urine collection will be stored for future batched testing for MG. Remnant urine from GC/CT testing may be used or the initial first catch specimen may be divided into two samples, as long as the minimum volume for GC/CT testing is met. See the MOPS for more information. Urine should also be collected for *M.gen* at the time of symptomatic urethritis (see Table 6.4.1)

- 6.3.14 **Nasal and oropharyngeal swab for** *Staphylococcus aureus*: nares and oropharynx will be swabbed and cultured for *S. aureus*, with antibiotic resistance testing if *S. aureus* growth present
- 6.3.15 **Oropharyngeal swab for commensal Neisseria species**. At baseline and month 12, all participants will undergo oropharyngeal swab for Neisseria species and TCN-resistance testing if Neisseria species are isolated.
- 6.3.16 **Stool specimen**: Stool samples from the first 50 participants living with HIV and 50 HIV- participants on PrEP who consent to collection will be obtained at baseline, 6 and 12 months for metagenomic resistome studies using 16sRNA amplification of TCN resistance genes. In the event that participants cannot provide a stool sample at the scheduled visit, they will have up to 2 weeks from the enrollment and 12-month visit to return the stool specimens for those visits, and up until two weeks after the 9-month visit to return the stool specimen for the 6-month visit.
- 6.3.17 **Rectal Swab for microbiome testing**: Rectal swabs will be collected and frozen for future microbiome analysis. These swabs may be self collected or collected by study staff.
- 6.3.18 **Hair collection**: Hair will be collected from all participants who consent to collection and who meet eligibility for hair collection (occipital hair length > 0.5 cm and absence of bleaching in area to be collected) See manual of procedures for details on hair collection

6.3.19 HIV testing and RNA data:

For PLWH: At entry and month 12, the most recent HIV RNA data available from clinical visits will be recorded

For participants on PrEP: At entry, the most recent HIV antibody or viral test results from clinical care will be recorded. If no test results available within the past 3 months, HIV testing should be obtained, consistent with standard of care monitoring for PrEP. At month 12, the most recent HIV antibody or viral load test results from clinical care will be recorded.

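### The 6.4.1 discard NOTE conflicts with the instructions to store the M. genitalium urine taken at symptomatic urethritis; read literally, it would selectively remove MG results from GC/CT-negative urethritis (exploratory objective 3)

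*Protocol*

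**What the plan says.** **Instructions to keep.** The Schedule of Events (Protocol 6.1) has the row "Urine stored for future MG testing (also at time of symptomatic urethritis". Section 6.3.13 says that when urine is taken for GC/CT, "a sample of this urine collection will be stored for future batched testing for MG"; it adds that MG urine is also to be collected at symptomatic urethritis and refers to Table 6.4.1 for this. Section 1.2.5 gives the reason: urine is taken every three months "as well as at the time of urethral symptoms, to evaluate for MG as the etiology of urethritis".

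**Instructions to discard.** Section 6.4.1 covers symptoms at a study visit that lead to empiric treatment. Its lead-in and the title of Table 6.4.1 both describe the contents as specimens for resistance testing. The table has two urine columns, one Zymo and one Hologic for M.gen, and both are ticked for urethritis. The NOTE says that "the resistance testing specimens (swabs/urine collection) should be held until definitive STI testing is available". It then gives two routes: "If STI testing indicates no infection, the specimens may be discarded", and "Alternatively, the site may send all specimens for storage". The next sentence closes the second route: "Specimens that are not associated with a confirmed STI will be discarded when the data management team confirms absence of STI". Only specimens whose STI status is uncertain are sent on to the BioHUB for testing.

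**The objective served.** Protocol 3.3.3 reads: "Evaluate the incidence of urethritis without identified bacterial etiology and the proportion which is associated with MG in each arm". The protocol synopsis and the SAP's protocol summary word the same objective in terms of nongonococcal, nonchlamydial urethritis and the share of urethritis with MG detected. The SAP specifies no analysis for it.

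**The concern.** Two instructions apply to one tube. One stores it for later MG testing; the other, on its face, discards it when no STI is confirmed. Confirmation at the symptomatic presentation means GC, CT and syphilis tests, so the discard rule would act on the episodes that objective 3 is about and spare the GC- or CT-positive ones.

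At stake is the MG share of GC/CT-negative urethritis by arm. If the tubes are gone, and no other MG specimen from the same episode was kept, that share cannot be recovered later. An MG figure computed from whatever was retained would then describe mainly GC/CT-positive urethritis, which is a different quantity.

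The pattern could also differ by arm. Protocol 10.2 anticipates reductions of 35% for GC and 65% for CT with doxycycline PEP, so the split of urethritis into GC/CT-positive and GC/CT-negative episodes need not be the same in the two arms. The documents do not say by how much, or in which direction the net effect would go.

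**Working it through.** The plan gives no figure on this point and no arithmetic applies. The check sets the passages side by side.

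1. **Is the urethritis MG urine the Table 6.4.1 specimen?** Yes. Section 6.3.13 refers to Table 6.4.1 for it, and the table has a column for it, ticked for urethritis.

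2. **Does the NOTE reach that specimen?** Read literally, yes. The NOTE addresses resistance testing specimens and names both swabs and urine. The lead-in and title place every column of the table under resistance testing. The mandatory discard sentence says only specimens, without qualification. No exception is written for M.gen. Nor is the label absurd for MG: 1.2.5 and objective 3.3.4 foresee later resistance work on MG-positive specimens.

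3. **Would MG count as a confirmed STI when discard is decided?** No. Section 6.4 is headed GC, CT and syphilis. The tests it requires at the presentation are GC/CT from three sites and syphilis serology. Under 6.3.13 MG testing is batched for later.

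4. **Does the storage option protect the tube?** Not fully. A site may send everything for storage, but the following sentence orders discard once absence of STI is confirmed. The BioHUB route applies only where STI status is uncertain.

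5. **Is there another MG specimen from the same episode?** By the wording of the plan, probably. Section 6.4.1 requires GC/CT urine at the symptomatic presentation. Section 6.3.13 stores an MG sample when GC/CT urine is collected, and allows remnant urine to be used. This is clear at quarterly visits; by its wording it also extends to interim visits.

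6. **What would be missing if that aliquot were not kept?**

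| Item | GC- or CT-positive urethritis | GC/CT-negative urethritis (no syphilis) |
|---|---|---|
| Episode recorded (6.3.5 history) | yes | yes |
| Table 6.4.1 MG urine under a literal NOTE | kept | discarded |
| MG status for objective 3 | available | missing |

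The incidence half of objective 3 does not depend on the tube, because 6.3.5 records treated urethritis in which neither gonorrhea nor chlamydia was found. Only MG status is at risk.

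7. **Can the loss be sized?** No. The documents give neither the expected number of urethritis episodes, nor the GC/CT-negative share, nor the MG prevalence, nor how sites apply the NOTE.

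**The case against.** The strongest reply is that the NOTE was never meant for the MG tube. Table 6.4.1 separates the Zymo urine from the Hologic M.gen urine. Section 6.4 is about GC, CT and syphilis, and the BioHUB work in 6.5.2 concerns those organisms and does not mention MG. The Hologic tube serves MG detection; resistance testing of MG is a later step on positives. On this reading the urine named in the NOTE is the Zymo urine alone, and the more specific storage instructions in 6.1 and 6.3.13 govern. Section 6.3.13 also refers to the manual of procedures, which is not available here and may settle the matter.

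This reading is reasonable, and the intent in 1.2.5, 6.1 and 6.3.13 is plainly to keep the urine. But 6.4.1 does not say so, and its title and lead-in point the other way. A site holding a GC/CT-negative tube has a written basis for discarding it.

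A reader might go further and infer that GC/CT-negative urethritis cannot be scored for MG at all, or that its denominator is lost. The documents do not support either. Section 6.3.13 provides a second MG aliquot from the same GC/CT urine, and 6.3.5 still records the episodes. Nor is there any basis in the documents for a percentage bias in the MG proportion; such a figure would rest wholly on assumed inputs.

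**Conclusion.** The conflict is real and should be reconciled. The loss is conditional: it occurs if sites apply the 6.4.1 NOTE literally to the Hologic urine and also keep no aliquot under 6.3.13. In that case MG status is missing selectively in GC/CT-negative urethritis, and the loss is irreversible. If either condition fails, MG can still be scored.

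Severity is low. One exploratory objective is affected, and only its MG component. The primary STI endpoint, the primary resistance objectives and safety do not depend on this specimen. The conclusion rests on the protocol text alone; the manual of procedures could narrow or remove the problem.

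**What to change.** Add one sentence to the 6.4.1 NOTE: the discard provisions do not apply to the Hologic M.gen urine listed in Table 6.4.1, which is kept for batched MG testing whatever the GC, CT and syphilis results. Put the same sentence in the manual of procedures if it is not already there.

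The cost is one sentence and storage for tubes that are already being collected, with no new procedure and no added burden on participants. The change is still useful after closure of enrollment, because follow-up continues to month 12 (Protocol 1.2.8) and any earlier tubes still held would be protected.

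Optional and editorial: align 3.3.3 with the synopsis and the SAP by referring to nongonococcal, nonchlamydial urethritis. An MG-positive case sits awkwardly in a group defined as having no bacterial cause identified, although the phrase can be read as none found by the GC/CT work-up.

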6.5 Testing for resistance in setting of STI diagnoses on study

6.5.1 Testing for tetracycline resistance among N. gonorroheae

Positive GC cultures for all participants will be sent to either the University of Washington Neisseria Reference laboratory for resistance testing led by our co-investigator, [name] at the UW/PHSKC STI program or the SFDPH Public Health Laboratory for testing by [name]. Both laboratories participate in the Strengthening the US Response to Resistant Gonorrhea (SURRG) program. GC isolates collected in Seattle and frozen isolates from San Francisco will be shipped to [name] on a monthly basis for agar dilution antimicrobial susceptibility to a panel of antimicrobials including tetracycline, as part of the Antimicrobial Resistance Lab Network (ARLN) supported by CDC. In addition, [name] laboratory will determine whether tetracycline MICs increases among the subset with repeat GC infections during follow- up.

6.5.2 Molecular testing for tetracycline resistance genes in C. trachomatis, T. pallidum and N. gonorrhoeae. DNA from positive NAAT tests for *C. trachomatis* and *N. gonorrhoeae* and from buccal or chancre/mucosal lesion swabs from those with newly diagnosed syphilis will be evaluated using established CRISPR/Cas9 techniques to screen against a comprehensive library of antibiotic resistance mutations order to establish rapid throughput methodology for the multicenter study. Tetracycline resistance will be assessed using FLASH (Finding Low Abundance Sequences by Hybridization)) targeted sequencing of antimicrobial resistance genes that will then be compared to an established antibiotic resistance database as well as evaluated for known tetracycline mutations that have been documented in the target STIs or closely related organisms⁶⁴. Molecular resistance testing will conducted at the San Francisco Chan-Zuckerberg Biohub under the supervision of collaborating investigator [name], who has extensive expertise in molecular diagnosis of mutations associated with antibiotic resistance mutations in *C. trachomatis* or *T. pallidum* will be investigated further, as clinically relevant tetracycline resistance has not been reported to date. The results will not be reported for use in clinical care as these methods are experimental and have not been validated for clinical care.

6.6 Treatment of STIs

Local clinic standards will be followed for the treatment of STIs diagnosed by laboratory tests or when identified syndromically. If doxycycline is used for treatment of an STI for an individual in the PEP arm, doxycycyline PEP will be held during treatment and resumed when treatment completed.

6.7 Qualitative interviews

A qualitative interview will be offered to a subset of participants assigned to take doxycycline, approximately 20 per site, during months 3-12, and up to one month after study completion. Qualitative interviews will also be offered to 10-20 providers at each of the sites A separate consent will be provided for these interviews.

6.8 Reenrollment of participants enrolled prior to 3/15/2020

Participants enrolled prior to the COVID pandemic will be re-enrolled starting 7/2020 with the same initial assignment. At time of re-enrollment, these participants will undergo all day 0 evaluations with the exception of the following

- Meningoccal vaccine history
- Medical & STI history
- Stool sample collection from first 50 PLWH and HIV uninfected on PrEP

7 ADVERSE EVENTS (AE) AND STUDY MONITORING

7.1 Adverse Event Collection Requirements

All AEs must be recorded on eCRFs if any of the following criteria have been met:

- All grade 2 and higher hematologic and hepatic laboratory abnormalities that are attributed to doxycycline in the opinion of the site investigator
- All AEs meeting SAE definition
- All grade 3 and 4 adverse events judged to be associated with doxycycline (possibly, probably, or definitely related)

Serious Adverse Events (SAEs)

An SAE is defined as any untoward medical occurrence that:

- Results in death
- Is life-threatening
- Requires inpatient hospitalization or prolongation of existing hospitalization
- Results in persistent or significant disability/incapacity
- Is an important medical event that may not be immediately life-threatening or result in death or

hospitalization but may jeopardize the patient or may require intervention to prevent one of the other outcomes listed in the definition above)

All AEs that are recorded must have their severity graded. To grade AEs, sites should refer to the Division of AIDS Table for Grading the Severity of Adult and Pediatric Adverse Events (DAIDS AE Grading Table), corrected Version 2.1, July 2017, which can be found on the DAIDS RSC website at https://rsc.tech-res.com/docs/default-source/safety/division-of-aids-(daids)-table-for-grading-the-severity-of-adult-and-pediatric-adverse-events-corrected-v-2-1.pdf

